### **5.11.1 Subject Withdrawal**

All enrolled subjects have the right to withdraw their consent at any time during this study. All data collected until the time of subject withdrawal will remain in the study database and will be used for analysis. Whenever possible, the site staff should obtain written documentation from the subject who wishes to withdraw his/her consent for future follow-up visits. If the site staff is unable to obtain written documentation, all information regarding the subject's withdrawal must be recorded in the subject's medical record. In addition, the appropriate eCRFs must be completed for the subject and clear documentation of the subject's withdrawal should be provided to the Sponsor.

### **5.11.2 Subject Discontinuation by Investigator**

An Investigator may discontinue a subject from the study, with or without the subject's consent, for any reason that may, in the Investigator's opinion, negatively affect the well-being of the subject. If a subject is withdrawn from the study, the Investigator will promptly inform the subject and Sponsor.

### **5.11.3 Lost to Follow-up**

A subject will be considered lost to follow-up if the subject cannot be reached after three (3) attempts to contact the subject for a follow-up visit. The site must document a minimum of three (3) attempts, and the final documented attempt should be made via registered letter.

## **5.12 Deviations to the Investigation**

A protocol deviation is defined as an event where the Investigator or study personnel did not conduct the study according to the clinical protocol. Deviations shall be reported to the Sponsor regardless of whether medically justifiable or taken to protect the subject in an emergency.

Except for a change that is intended to eliminate an immediate hazard to a subject, the protocol will be followed as described. Subject specific deviations and non-subject specific deviations, (e.g. unauthorized use of a study device outside the study, unauthorized use of a study device by a physician, etc.) will be reported. Investigators will also adhere to procedures for reporting study deviations to their IRB/EC in accordance with their specific IRB/EC's reporting policies and procedures.

Sites with a high rate of protocol deviations will be closely evaluated and are expected to implement corrective actions to prevent further deviations. If a site demonstrates persistent deviations, as described above, the site may be terminated.

Some information collected in this study is not essential to the study endpoints and will not be considered a deviation if absent.

### **5.12.1 Discontinuation by IRB/EC**

The IRB/EC may choose to discontinue the study at any center(s) for which they granted approval if:

- The research study is not conducted in accordance with the IRB/EC's requirements.
- The research study indicates unexpected serious harm to subjects.

### **5.12.2 Study Discontinuation by Sponsor**

The Sponsor may choose to discontinue the study should the Sponsor discover additional information during the study that may cause harm to subject safety.

If the study is terminated prematurely or suspended, the Sponsor will promptly inform all clinical Investigators of the termination or suspension and the reason(s) for this. The IRB/EC will also be informed, either by the Sponsor or Investigator if a local IRB/EC is utilized, promptly and provided with the reason(s) for the termination. If applicable, regulatory authorities will be informed. Enrolled subjects will be asked to complete all remaining study visits and the subject will then be seen by the treating physician according to standard care following intracranial aneurysm treatment.

Any investigator who is discovered during monitoring to have not reported neurologic adverse events may be terminated from the study at the discretion of the Sponsor

## **6 ADVERSE EVENTS**

The following adverse events will be collected during the course of the study on the eCRFs.

- All Adverse Events (AE) with an underlying neurological cause (Neurological Adverse Events)
- All Device Related Adverse Events
- All Procedure Related Adverse Events
- All Serious Adverse Events (SAE's)

Adverse event status will be evaluated throughout the study. These will include new events occurring after the point of consent in the study until a subject exits the study. Subjects who are enrolled, underwent surgery to implant to study device but did not have the Pipeline™ device implanted for any reason will be followed for 30 days and relevant safety events will be collected. Investigators must obtain all information available to determine the causality and outcome of the AE and to assess whether it meets the criteria for classification as a serious and/or unexpected event requiring notification to the Sponsor, regulatory agency, and as applicable, IRB/EC, within the specified reporting timeframe. AEs will be categorized using the definitions in **Section 6.1**.

All study AEs, as well as the treatment and follow-up required, should be documented in the subject's medical records and in the eCRF. All study AEs will be followed by the Investigator until resolution or until the end of the 3-year follow-up. A list of potential anticipated adverse events is provided in **Section 10.2**.

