### **5.4 Procedure**

Subjects must undergo the device placement procedure within 60 calendar days of completion of all baseline assessment tests and procedures. The status of the target IA may change between the screening evaluation and the procedure that may change the risk profile of the study procedure.

Therefore, a pre-treatment (baseline) angiogram will be required before the procedure to confirm that the study procedure can be safely carried out and to collect precise images for the core laboratory. If in the unlikely event that the subject is deemed to be ineligible, the subject will not require any study follow-up.

Each subject will undergo a neurologic examination and assessment using NIHSS. The subject will be tested for antiplatelet response (e.g. using VerifyNow (Accumetrics)). Periprocedural heparin per institutional protocol is required. Prior to inserting the study device, the activated clotting time (ACT) should be checked and adjusted as clinically appropriate. Further ACTs will be checked per standard practice.

The physician will place and deploy the appropriate number of Pipeline™ device braids at the target site to treat the IA.

Post-treatment, the investigator will assess device occlusion, placement and overall status of the aneurysm. Angiograms in the anteroposterior (AP), lateral, and working positions will be obtained. The Investigator will take necessary steps to ensure that pre- and post-placement angiograms are performed using similar views, magnifications, and contrast amount to ensure valid “before/after” comparisons. However, these angiographic details will not be collected in case report forms (CRFs). The Investigator will submit procedural angiograms to the imaging core laboratory. The Investigator will ensure that subject identifiers are removed from all submitted images. Image files/CDs should be labeled with the subject’s study ID number.

Medications appropriate for general anesthesia will be administered using standard hospital practice. Platelet inhibition and aggregations status pre- and post-surgical intervention, including antiplatelet antibodies will be evaluated. All medication use during surgery and immediately post-procedure will be documented. Radiation exposure will be recorded as absorbed radiation dose and cumulative fluoroscopy time will be recorded.

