### 9.3 Analysis Population

The analysis population will be comprised of the results from 141 treated subjects. Results will be presented based on two populations:

*Intention to Treat* (ITT): defined as all enrolled subjects in whom deployment of the Pipeline™ device was attempted. It is possible that the Pipeline™ device may not reach the target site and the **operator** would not attempt to deploy it, in the rare event that happens, that subject will not be considered part of the ITT population.

*Full Analysis Set* (FAS): defined as a subset of ITT including only those in whom the Pipeline™ device was implanted.

*Per protocol* (PP): defined as all enrolled subjects, had the Pipeline™ device implanted, and were followed without any major protocol deviations.

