### 9.4 Analysis of the Primary Safety Endpoint and Objective

The primary safety endpoint is the incidence of major stroke or neurological death at 1-year post-procedure in the ITT population. The primary safety objective is to determine if the incidence of major stroke in the territory supplied by the treated artery or neurological death at 1-year of the study procedure is below a pre-specified threshold of 15% with 97.5% confidence.

In the previous Pipeline™ device IDE trial (PUFs), the safety endpoint of occurrence of ipsilateral major stroke or neurological death was evaluated. The most commonly used endovascular approach for small and medium, wide-necked IAs is stent-assisted coil embolization. Published literature on stent-assisted coiling for mainly small and medium wide-necked IAs (Table 1) demonstrates rates of procedure/device-related neurologic deficit ranging from 3.9% to 9.2% and rates of procedure/device-related mortality rates ranging from 0% to 6.8%, yielding combined procedure-/device-related morbidity and mortality rates up to 16%. Although technological advancements have been made, subjects eligible for PREMIER have few reasonable alternatives for sustained occlusion. They face a risk of often-fatal spontaneous bleeding without treatment. They also face a high rate of stroke or death with currently available treatments such as neurosurgery or stent-assisted coiling. A procedure with a high effectiveness rate and perioperative stroke/death rate whose upper confidence limit is <15% represents a significant advance for this patient population. The lack of reasonable alternatives justifies the proposed safety study success parameters.

The 1-sided 97.5% confidence interval will be calculated using the exact Clopper-Pearson method. Results will be based on the Full Analysis Set. Subjects who fail to complete the 1-year post-procedure evaluation period and do not experience the events of interest will be counted as not having experienced the event.

A sensitivity analysis will be prepared using an adjusted analysis model, censoring subjects who withdraw prior to 1-year and did not experience the events of interest.

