### **9.9 Analysis of the Additional Data**

The device-related neurologic adverse event rate at 1 year post-procedure will be tabulated for the ITT population and presented using counts, percentages, and 2-sided 95% exact binomial confidence intervals. The mRS score at 1 year will be dichotomized ( $\geq 2$  vs.  $< 2$ ) and summarized using counts, percentages, and 2-sided 95% exact binomial confidence intervals. Aneurysm occlusion will be tabulated for the Full Analysis Set and presented using counts, percentages, and 2-sided 95% exact binomial confidence intervals. The proportion of subjects who experience recurrence and require retreatment will be summarized using counts, percentages, and 2-sided 95% exact binomial confidence intervals. Procedure time, radiation exposure (dosage and time) and number of Pipeline™ devices utilized will be summarized using descriptive statistics (N, mean, median, standard deviation, minimum and maximum value, and 95% 2-sided confidence limits).

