## **9.11 Safety Analysis**

All analyses regarding subject safety will be predicated on the ITT population. The number and proportion of subjects experiencing each type of event will be summarized overall and by site. Only treatment emergent events will be included in the analysis, i.e., events that began or worsened after enrollment.

The safety of the procedure will be measured by the incidence of adverse events. The following sections describe how the safety endpoints will be analyzed.

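### Subjects with an attempted but failed implant count in the ITT set for 1-year safety, but have no planned contact after Day 30, so ITT 1-year safety rates can err only downward

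*Combined protocol and SAP*

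**What the plan says.** **Who is in each set.** Section 9.3 has ITT "defined as all enrolled subjects in whom deployment of the Pipeline™ device was attempted"; implantation is not required. The Full Analysis Set (FAS) is "defined as a subset of ITT including only those in whom the Pipeline™ device was implanted". An attempted but failed implant is thus in ITT and outside FAS.

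**How long they are followed.** Section 6 covers enrolled subjects who went to the procedure and "did not have the Pipeline™ device implanted for any reason will be followed for 30 days and relevant safety events will be collected". Section 4.2 ties participation of up to 3 years, including the 180-day and 1-year visits, to eligible subjects treated with the device.

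**Which outcomes use ITT.**
- Section 9.4: "The primary safety endpoint is the incidence of major stroke or neurological death at 1-year post-procedure in the ITT population". The same section then says of the test: "Results will be based on the Full Analysis Set".
- Section 9.9: "The device-related neurologic adverse event rate at 1 year post-procedure will be tabulated for the ITT population".
- Section 9.11: "All analyses regarding subject safety will be predicated on the ITT population".

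**How missing time is handled.** Section 9.4 counts a subject with no completed 1-year evaluation and no event as free of the event. Section 9.1 does the same for a missed 1-year visit unless a stroke or death is known. The sensitivity analysis in Section 9.4 censors subjects who withdraw before 1 year; it does not mention subjects whose planned follow-up ends at 30 days.

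**Later implant.** Under Section 5.4 a subject not treated at the first procedure may return for implantation, and Day 0 is then the implant date.

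**The concern.** A 1-year rate needs subjects who are observed for a year. For failed implants the plan ends observation at 30 days by design, so this is not dropout that better retention could cure. These subjects stay in the ITT denominator, while any event of theirs after Day 30 reaches the numerator only if it happens to become known. Their procedures did not go as planned, so it is hard to assume that they are at lower risk than the rest.

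The default of no event makes the error one-directional. The sensitivity analysis that should expose it is written for withdrawals, and a planned exit at 30 days is not a withdrawal. Time that was never observed cannot be recovered at the analysis stage, so the remedy has to be in place prospectively.

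**Working it through.** **1. Unobserved time.** Planned follow-up is 30 days (Section 6) and the outcome window is 365 days (Sections 9.4 and 9.9).
- Covered: 30/365 = 8.2%.
- Not covered: 365 − 30 = 335 days; 335/365 = 91.8%.

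Events up to Day 30 are collected, and Section 6 follows events already recorded until resolution. The gap concerns new events after Day 30.

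**2. Reproducing the plan's figure.** Section 9.2 uses a one-sided 97.5% Clopper-Pearson bound against 15%. The upper limit is U(x, n) = the 0.975 quantile of Beta(x + 1, n − x). With x = 0.09 × 141 = 12.69 left fractional, U = 14.99%. The smallest n giving U < 15% at 9% is 141, as in Table 7. The same rule returns the other Table 7 sizes (52, 63, 80, 104).

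**3. Pass limit if the ITT set has exactly 141 subjects.**
- 12 events: 12/141 = 8.5%, U = 14.39%, pass.
- 13 events: U = 15.25%, fail.

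**4. Effect of k failed implants.** The documents give no value for k. I assume 1 to 7, which is 0.7% to 5.0% of 141. If the k subjects are among the 141, the extreme case in which each has an unseen event gives:

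| Events observed | k | Total | U | Result |
|---|---|---|---|---|
| 12 | 1 | 13 | 15.25% | fail |
| 10 | 2 | 12 | 14.39% | pass |
| 10 | 3 | 13 | 15.25% | fail |
| 7 | 5 | 12 | 14.39% | pass |
| 7 | 7 | 14 | 16.10% | fail |

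The last row needs all seven subjects to have an event, which is a bound and not an expectation.

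**5. Is 141 the right ITT denominator?** Sections 4.1 and 9.3 give 141 as the number of treated subjects. If treated means implanted, failed attempts come on top and ITT is 142 to 148 for the same k. For 13 events:
- n = 142: U = 15.15%, fail.
- n = 143: U = 15.04%, fail.
- n = 144: U = 14.94%, pass.
- n = 148: U = 14.55%, pass.

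The limit of 12 events therefore holds only for an ITT set of about 141 to 143.

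**6. If FAS governs the primary test.** Failed implants leave both numerator and denominator, so the follow-up gap does not reach the test. The choice of set still moves the bound slightly. With 141 in ITT and 12 events, all in implanted subjects, U on FAS is 14.49% for k = 1, 14.91% for k = 5 and 15.12% for k = 7.

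**The case against.** The strongest reply is that little hangs on this. Section 9.4 says that results are based on FAS, and the secondary safety endpoints in Section 9.7 use FAS too. The one 1-year rate that is on ITT without contradiction is device-related and is listed as additional data. Section 6.1 requires a strong temporal relationship to the device for that label, so with nothing left implanted few new events after Day 30 would qualify. Section 9.11 summarises adverse events on ITT but sets no 1-year rate. Some of these subjects return for implantation and join the normal schedule.

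Most of this stands, and it limits the size of the problem. It does not remove it. Section 9.4 names both sets, so FAS cannot be taken as settled. Section 6.1 counts the delivery system as part of the device, so a failed deployment can cause a device-related event. A subject who is never implanted stays in the ITT denominator for Section 9.9.

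It could also be said that the 30-day rule was considered, because the summary of changes records that follow-up of non-implanted subjects and the analysis populations were both revised after a regulator's letter. That does not show that the two were aligned with each other.

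A reader might infer more than the documents support:
- *That these subjects are not measured at all, or that the ITT rates cannot be produced.* Events to Day 30 are collected, known later strokes and deaths still count, and the counting rule yields a number. The number may be too low.
- *That a 13th event always turns a pass into a fail.* Step 5 shows that this depends on the ITT size, which is not fixed.
- *That about 20% of their events fall after 6 months.* The 80% figure in Section 9.6 is a planning assumption for the monitored cohort and says nothing about subjects without an implant.
- *That Section 5.4 contradicts Section 6 by requiring no follow-up after ineligibility at the pre-treatment angiogram.* The two conflict only if that angiogram counts as surgery to implant. Read naturally, they describe different groups, and a subject with no deployment attempt is outside ITT anyway.

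**Conclusion.** The mismatch holds. ITT includes failed implants, planned contact with them ends at Day 30, and at least one 1-year safety rate is on ITT. Because unobserved subjects are counted as event-free and the censoring analysis does not cover them, an ITT 1-year safety rate can be biased only downward.

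The size is likely small. It rests on an assumed 1 to 7 failed implants, since the documents state no rate. The primary test is affected only if ITT governs it and the event count is near the limit, about 8.5% observed if ITT is 141. That region is not remote, because the trial is sized on a 9% rate, but with an event rate near 5% the conclusion would change only in the extreme case in step 4. The change is worth making because it is cheap and the lost information cannot be recovered later.

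**What to change.** 1. In Sections 6 and 4.2 and in Table 5, collect adverse events, NIHSS and mRS at 180 days and 1 year after the attempt in every ITT subject who was not implanted, without study angiography. Section 6 may keep its 30-day rule for subjects with no deployment attempt, who are outside ITT.
2. State that a subject implanted at a later procedure moves to the normal schedule, with Day 0 at implant as in Section 5.4.
3. In Section 9.4, extend the ITT safety sensitivity analysis so that a non-implanted subject still unobserved at 1 year is censored at last contact, in addition to the analysis that counts the subject as event-free. Report the number of such subjects.
4. In Section 9.4, name one population for the primary safety test and reconcile the ITT and FAS statements.

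The cost is protocol and consent wording, and two non-invasive follow-up contacts in what is probably a handful of subjects. Items 3 and 4 are text changes only.

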## 6.1 Adverse Event Definitions

An *Adverse Event* (AE) is defined as any untoward medical occurrence, unintended disease or injury, or untoward clinical signs (including abnormal laboratory findings) in subjects, users or other persons, whether or not related to the investigational medical device. (ISO 14155:2011 3.2)

NOTE 1: This definition includes events related to the investigational medical device or the comparator.

NOTE 2: This definition includes events related to the procedures involved.

NOTE 3: For users or other persons, this definition is restricted to events related to investigational medical devices.

An *Adverse Device Effect* (ADE) is defined as an adverse event related to the use of an investigational medical device. (ISO 14155:2011 3.1) The investigational medical device for this study is the Pipeline™ device used during the procedure (Day 0).

NOTE 1: This definition includes adverse events resulting from insufficient or inadequate instructions for use, deployment, implantation, installation, or operation, or any malfunction of the investigational medical device.

NOTE 2: This definition includes any event resulting from use error or from intentional misuse of the investigational medical device.

A *Serious Adverse Event* (SAE) is defined as an adverse event that

- a) Led to death,
- b) Led to serious deterioration in the health of the subject, that either resulted in
  - a. A life-threatening illness or injury, or
  - b. A permanent impairment of a body structure or a body function, or
  - c. In-subject or prolonged hospitalization, or
  - d. Medical or surgical intervention to prevent life-threatening illness or injury or permanent impairment to a body structure or a body function,
- c) Led to fetal distress, fetal death or a congenital abnormality or birth defect (ISO 14155:2011 3.37)

NOTE: Planned hospitalization for a pre-existing condition, or a procedure required by the CIP, without serious deterioration in health, is not considered a serious adverse event.

A *Serious Adverse Device Effect* (SADE) is defined as an adverse device effect that has resulted in any of the consequences characteristic of a serious adverse event. (ISO 14155:2011 3.36)

An *Unanticipated Serious Adverse Device Effect* (USADE) is defined as a serious adverse device effect which by its nature, incidence, severity or outcome has not been identified in the current version of the risk analysis report. (ISO 14155:2011 3.42)

An *Unanticipated Adverse Device Effect* (UADE) is defined as any serious adverse effect on health or safety or any life-threatening problem or death caused by, or associated with, a device, if that effect, problem, or death was not previously identified in nature, severity, or degree of incidence in the investigational plan or application (including a supplementary plan or application), or any other

unanticipated serious problem associated with a device that relates to the rights, safety, or welfare of subjects. (21 CFR 812.3 (s))

*Severity:*

- Mild: No limitation of usual activities, no therapy or only symptomatic therapy required to treat the injury or illness.
- Moderate: Some limitation of usual activities or specific therapy is required.
- Severe: Inability to carry out usual activities, hospitalization, emergency treatment, life threatening events, or death.

*Relatedness:*

- Study Disease-related: Event is clearly attributable to the underlying study disease state with no temporal relationship to the device, treatment, or medication.
- Concomitant disease-related: Event is clearly attributable to the underlying concomitant disease state with no temporal relationship to the device, treatment, or medication.
- Procedure-related: Event has a strong temporal relationship to the procedure (Day 0). This includes AEs attributable to any device(s) other than the Pipeline™ device used at procedure (day 0), such as access devices, delivery microcatheters, non-ionic contrast, guidewires, or any other adjunctive, approved/cleared device for treatment of intracranial aneurysms.
- Device-related: Event has a strong temporal relationship to the study device, and alternative etiology is less likely.
  - Pipeline™ device used at the procedure (Day 0) including the braid and the delivery system.
  - If the event is related to the Pipeline™ device used at a procedure other than the procedure (Day 0), it should be characterized with an event relationship of “Non-index procedure related”.

All events considered “device-related” will be further characterized as either:

- Anticipated: When the event was previously identified in nature, severity or degree of incidence in the investigational plan. Or
- Unanticipated: When the event was not previously identified in nature, severity or degree of incidence in the investigational plan.
- Non-index procedure related: This includes AEs attributable to any device(s) used at procedures other than day 0, such as access devices, delivery microcatheters, non-ionic contrast, guidewires, or any other adjunctive, approved/cleared device for treatment of intracranial aneurysms. This may include commercially available Pipeline™ devices used in procedures other than at Day 0 or those used on non-target lesions.
- DAPT-related: Event is clearly attributable to dual antiplatelet therapy (DAPT) with no temporal relationship to the device, treatment, or medical history.
- Unknown: Event relationship cannot be attributed to any of the above categories and remains undetermined.

